Primary outcomes	Expected or unexpected adverse events during the follow-up period. Examples of expected adverse events (but not restricted): asymmetry, breast pain, tissue atrophy, calcification, capsular contracture, rupture, delay in wound healing, extrusion, hematoma, infection, inflammation or irritation, lymphedema or lymphadenopathy, displacement, necrosis, anesthesia, hypoesthesia, paraesthesia or hyperesthesia of the breast or nipples, palpability, ptosis, ecchymosis, seroma, skin rash, visibility, wrinkling and undulation, cysts and nodules. The events of greatest interest initially are the events that cause the need for any reoperation, removal of the implant, removal of the implant with replacement or removal of the implant without replacement, events directly related to the presence of the implant (capsular contraction grade III / IV, implant, etc.).
Secondary outcomes	Breast self-assessment questionnaire (BEQ-Brazil), Rosenberg global self-esteem scale, patient satisfaction, researcher satisfaction.
Duration of the study	Each participant will be followed up to 10 years.
Allocation of treatment	As the participants will be invited to participate after the implants, the research protocol does not foresee any interference of the research procedures in the choice of the type or size of the implants as well as in the surgical technique used.
Masking / Blinding	There will be no masking / blinding.
Statistical analysis plan	For the primary endpoint, the risk / rate of groups of adverse events and specific events and their respective confidence intervals. These estimates will be made taking into account both the implant and the patient as unit of observation. For the secondary objectives changes in scores over time will be used to construct gross and adjusted correlation trajectories.
Minimum Sample	700 participants divided into 2 groups formed by the type of implant. There will be 350 volunteers with implants with textured surfaces and another 350 with implants with polyurethane surface.

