2.3. Expectation of expected adverse events

Technical reports provided by the FDA used for silicone breast implant registries from different manufacturers indicate a variety of risks from implant or surgery-related events. The most frequent event in all reports, consistent with the literature in general, is capsular contracture. Capsular contracture, when intense, is also the most frequent indication of implant removal. Below is a comparison of risks of events of interest by major interest groups and by different manufacturers. However, it is not possible, through the data from these reports to verify if there are differences between the different types of implants, nor what prognostic elements determine

Silimed Indústria de Implantes Ltda

[name]

[contact] **[contact]

www.silimed.com.br • [contact] • facebook: silimed international/brasil

the events in the different interest groups.

Cumulative incidence by type of event, implantation indication and implant brand (data retrieved from technical registration reports).

	Natrelle (Textured Surface - in 7 years)%		Natrelle (Textured Surface - in 3 years)%		Sientra (any surface - in 3 years)%		Mentor (any surface - in 3 years)%	
Event	Augmentation	Reconstruction	Augmentation	Reconstruction	Augmentation	Reconstruction	Augmentation	Reconstruction
Any Complication	31,0	53,0	-	-	-	-	-	-
Any Reoperation	22,4	45,2	12,7	21,0	12,6	34,9	15,4	27,0
Removal of the implant with or without replacement	12,6	29,3	-	-	-	-	-	-
Removal of the implant without replacement	1,2	5,3	0,5	2,9	1,2	7,0	2,3	5,7
Removing the Implant with Replacement	11,5	25,2	5,0	14,9	4,6	19,1	2,8	7,4
Capsular contracture grade III / IV	6,1	10,7	2,1	7,3	6,0	8,8	8,1	8,3
Implant rupture	6,9	8,9	1,3	0,0	3,0	0,0	0,0	0,0

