5.3.1. Inclusion Criteria

Inclusion criteria: (1) provide free informed consent, (2) female at birth, (3) 18 years or older, (4) have received breast implant(s) for indication of primary augmentation up to 14 days prior, (5) have received breast implants with a textured surface or breast implant with a polyurethane foam-coated surface of the brand Silimed®, (6) ability to comply with the protocol for the entire follow-up time.

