5.9. Statistical analysis plan

The statistical analysis will be divided into two parts, one descriptive and one analytical. The descriptive part will consist of showing counts and fractions of categorical variables and central tendencies (mean + standard deviation or median + interquartile range) of continuous variables recorded at the beginning of the follow-up by the groups of major interest. The groups of major interest are formed by the indication of implantation and the type of implant (primary augmentation
Silimed Indústria de Implantes Ltda

[name]

[contact] **[contact]

www.silimed.com.br • [contact] • facebook: silimed international/brasil

with textured surface implant, primary augmentation with polyurethane foam-coated surface implant). In addition, for the purpose of exploring heterogeneity this approach will also be done by participant center.

The initial statistical analysis for the analytical part is to estimate the risks (cumulative probabilities up to a follow-up time) and their respective confidence intervals of unwanted (expected and not expected) events in general and interest-specific ones (e.g. capsular contracture in the textured implants group, in the polyurethane implants group, mild events, serious events, events with probable causality, etc.), as well as events of different intensities (mild, moderate, severe, etc.). The accumulated risks up to the first events in the period of interest will be estimated through the Kaplan-Meier estimator. This analysis should consider the patient as an observation unit, and then the same approach will consider the breast as an observation unit.

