The incidence density estimate (incidence rate = (number of events / person-year) x 100) over a period of time, accumulated from the beginning of the follow-up and decomposed by the year of follow-up, will have the same rationale as the risk estimate, in the same patient groups and types of events, and will disregard the difference between incidence and recurrence of events as well as the period in which the participants were not at risk. This approach will allow estimating the incidence over a cumulative period (e.g. from the beginning of the follow-up) as well as decomposing the incidence into different periods (e.g. incidence in the second or third year of follow-up). In the same way as the previous approach, this analysis will consider a volunteer as an observation unit, then the same approach will consider a breast as the unit of observation.

The additional strategy for estimating the "hazard" for each of the most significant adverse events is to use a multiple model that allows the adjustment of each group's "hazard" for each event of major interest in the follow-up period by elements that could modify the prognosis of the volunteers or confuse the "hazard" estimate. These elements are described above in the section on "descriptive characteristics that could interfere with the prognosis".

Secondary outcomes, related to the desired effect of implants, that will be measured as continuous scales will be analyzed as trajectories over time. To this purpose, the individual crude trajectories of each participant will be verified, then the means / medians and their respective confidence intervals will be estimated at each follow-up time, and finally the marginal trajectories adjusted for correlation of each group (formed by each type of implant - textured and polyurethane)

Silimed Indústria de Implantes Ltda

[name]

[contact] **[contact]

www.silimed.com.br • [contact] • facebook: silimed international/brasil

will be estimated, always having the follow - up time as a predictor.

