5.10. Minimum sample size

The minimum sample size was estimated considering the variations of safety outcomes considered clinically relevant in the primary breast augmentation groups in different studies with a 3-year follow-up. It would be interesting to consider event risk estimates over 10 years because of the study follow-up plan. However, the risks available in the literature are rarely reported in 10 years or it is not possible to be sure that all volunteers have been followed for 10 years or more. It was possible to find only one study with a 9-year accumulated risk assessment with Silimed® products [36], which indicates that the risks of implant rupture are 4.3% and 1.2%, that the capsular contracture risks are 12.0% and 14.4%, that the risks of removal of the implant were 13.9% and 36.4%, and that the risks of any reoperation were 22.2% and 47.9%, always in the primary augmentation and primary reconstruction groups respectively. In this way, we also considered the risk accumulated in 3 years of previous studies that were used to register similar products and that the risks between the implant types are equivalent.

The events considered relevant were: need for reoperation for any reason, removal of the implant without replacement, removal of the implant with replacement, capsular contraction grade III or IV and implant rupture initially having a study of 3 years of follow-up and as a measure of interest to be estimated at a given time event, in the example of 3 years of follow-up. We used the epiDisplay package of R-project software that has a function with a formula that indicates the probability of the event of interest in the population and the formula returns the minimum sample size (N). [37] In addition, we determined the additional arguments of the formula, which are the population size for which the results would be inferred as infinity, the significance as 5%, and the difference between the estimated probability and one of the limits of the confidence interval (accuracy) as follows: if the probability to be estimated between 0.30 and 0.70, the desired accuracy = 0.1; If the probability is between 0.10 and 0.30, or between 0.70 and 0.90, the desired accuracy would be = 0.05; If the probability to be estimated is less than 0.10 or greater than 0.90, the desired accuracy would be half the probability or half of the probability respectively.

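### Breast-level risks and rates in section 5.9 need intervals that allow for two breasts in one woman; the plan names no interval method and does not ask for this

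*Combined protocol and SAP*

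**What the plan says.** The Executive Summary makes both units part of the primary endpoint: "These estimates will be made taking into account both the implant and the patient as unit of observation". Section 5.9 carries this out twice. For cumulative risks to the first event, estimated by Kaplan-Meier with confidence intervals: "This analysis should consider the patient as an observation unit, and then the same approach will consider the breast as an observation unit". For incidence rates: "this analysis will consider a volunteer as an observation unit, then the same approach will consider a breast as the unit of observation". The rates also pool first and repeat events; they "will disregard the difference between incidence and recurrence of events as well as the period in which the participants were not at risk".

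Section 5.9 names no variance or interval method for either unit. Its adjusted hazard model has no clustering term either. Correlation is mentioned once, for the secondary continuous scales: "finally the marginal trajectories adjusted for correlation of each group".

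A woman may contribute one or two implants, since section 5.3.1 requires participants to "have received breast implant(s) for indication of primary augmentation up to 14 days prior". Section 5.11 repeats the final-report analyses every year where numbers allow. It also tests risks against alarm limits at the 1% level, without saying whether those risks are per woman or per breast.

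**The concern.** A woman's two breasts share one body, usually one surgeon and one operation, and the prognostic factors listed in section 5.4.2, such as comorbidities and placement technique. Positive correlation between their events is therefore plausible. The standard Kaplan-Meier interval (Greenwood) and the standard rate interval (Poisson) assume independent units. Moving from women to breasts by an identical procedure counts up to twice as many units as there are independent women, and the error bars shrink too far.

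The study's purpose is estimation, and section 5.10 sizes it on interval width. Breast-level estimates belong to the primary endpoint for each implant type and would recur in the annual reports. At stake is overstated precision in those estimates, and in any breast-level comparison built on them.

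**Working it through.** **Inputs from the documents.** One or two implants per woman (5.3.1); 350 women per implant type, 5% significance and 40% loss over 10 years (5.10).

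**Assumed, because the documents give no value.** rho, the correlation between event indicators in a woman's two breasts, from 0.1 to 0.7; b, the share of women with two implants, 1 or 0.8.

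**Step 1: the plan's own figures.** Section 5.10 uses n = z²p(1−p)/d². For p = 0.10 and d = 0.05, 3.8416 × 0.09 / 0.0025 = 138.3 (plan: 138). For p = 0.18, 3.8416 × 0.1476 / 0.0025 = 226.8 (plan: 227). These sizes count women and contain no design effect, which is right for a patient-level proportion. The plan has no breast-level interval to reproduce.

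**Step 2: variance per breast.** N women give M = N(1+b) breasts. With breast-level risk p, the variance of the event count is p(1−p)[M + 2bN·rho]. Relative to independent breasts the inflation is

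D = 1 + 2b·rho/(1+b), which is 1 + rho when b = 1.

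The ordinary interval is too short by 1 − 1/√D, and its true coverage is 2Φ(1.96/√D) − 1.

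| rho | D (b = 1) | too short | coverage | D (b = 0.8) | too short | coverage |
|---|---|---|---|---|---|---|
| 0.1 | 1.10 | 4.7% | 93.8% | 1.09 | 4.2% | 94.0% |
| 0.3 | 1.30 | 12.3% | 91.4% | 1.27 | 11.1% | 91.8% |
| 0.5 | 1.50 | 18.4% | 89.0% | 1.44 | 16.8% | 89.7% |
| 0.7 | 1.70 | 23.3% | 86.7% | 1.62 | 21.5% | 87.6% |

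At rho 0.5 with all women bilateral, the 700 breasts in one group carry the information of 700/1.5 = 467 independent breasts.

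**Step 3: check with censoring.** A simulated breast-level Kaplan-Meier analysis used 350 bilateral women, 40% loss over 10 years shared within a woman, and 2,000 runs. The breast-level risk was set at 12% at 10 years for illustration only. For event correlations of 0, 0.26, 0.52 and 0.76:

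- The Greenwood standard error stayed at 0.0140 to 0.0141, while the actual standard error was 0.0142, 0.0157, 0.0173 and 0.0179.
- Greenwood coverage was 94.5, 92.4, 89.1 and 86.8%.
- A variance clustered on the woman kept coverage between 94.1 and 95.0%.
- The mean estimate stayed at 11.9 to 12.0%, so clustering does not shift the point estimate.

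**Step 4: incidence rates.** The same argument applies per breast. Because recurrences are pooled, a woman can also contribute several correlated events to the patient-level rate, so a simple Poisson interval, if used, can be too narrow there as well. The size depends on how much women differ in event-proneness, which the documents do not give.

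**The case against.** **This is an omission, not a wrong method.** The plan names no interval, and repeating the approach per breast can be read as covering only the estimator, groups and event types. A clustered interval would contradict nothing in 5.9. This stands, so the point is conditional: a reader might infer that the plan prescribes intervals that treat breasts as independent, but it does not say so. The request remains, because 5.9 is the only analysis plan, it provides for correlation elsewhere but not here, and the ordinary interval is the natural result of carrying a patient-level method over.

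**Little depends on breast-level precision.** The sample size counts women, the patient-level analysis comes first, and the alarm's unit is not stated. All true. But the Executive Summary still places implant-level estimates in the primary endpoint.

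**Withdrawal limits the effect.** Section 6.5.1 lets the investigator or sponsor withdraw a woman after implant removal, which would cut off later events in her other breast. The same section asks that outcome data still be collected after discontinuation. The two statements need reconciling. The effect is smaller if follow-up ends after a first event, but the documents do not allow the reduction to be quantified.

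**Accuracy targets.** A reader might infer that breast-level intervals miss the targets in 5.10, or that they safely meet them. The documents support neither reading. For risks between 0.10 and 0.30 the target is fixed: "If the probability is between 0.10 and 0.30, or between 0.70 and 0.90, the desired accuracy would be = 0.05". Below 0.10 it is half the risk, so the target itself depends on the breast-level risk. Section 5.10 does not say whether its 9-year risks of 12.0% (contracture) and 4.3% (rupture) are per woman or per breast. If 4.3% is per woman, all women are bilateral and there is no loss, clustered half-widths at rho 0.1, 0.3, 0.5 and 0.7 are 1.16, 1.33, 1.52 and 1.73 points, against targets of 1.14, 1.28, 1.45 and 1.67: a narrow miss each time. If 4.3% is per breast, with 40% loss, they are 1.75, 1.88, 2.01 and 2.15 against 2.15. The answer turns on a unit that is not given.

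**Conclusion.** The point holds in conditional form. If ordinary intervals are used per breast, they overstate precision by an amount that depends on rho and on the share of bilateral women. Neither is in the documents. Over the assumed range, the shortfall in width runs from about 4 to 23% and coverage from about 94 down to 87%. At rho 0.1 this is negligible; at 0.5 or above it is material for a study built on estimation. Confidence is high that the variance is unspecified, and lower on the size of the effect.

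A reader might go further and infer that the primary safety results as a whole are unreliable. The documents do not support that: clustering leaves point estimates, patient-level Kaplan-Meier intervals and the sample size of 350 women per group unaffected. No claim is made about the 5.10 accuracy targets at breast level. The point is worth fixing, but it is not fatal.

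**What to change.** Add to section 5.9 that a variance clustered on the woman, either robust or from a bootstrap that resamples women, will be used for:

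1. breast-level Kaplan-Meier intervals;
2. incidence-rate intervals, at both levels because recurrences are pooled within a woman;
3. any hazard model fitted per breast.

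In section 5.11, state the unit for the 1% alarm; if it is run per breast, use the same variance.

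The cost is one or two sentences and a standard software option. Data collection, sample size and point estimates do not change. The downside is that these intervals become wider when events are positively correlated; if the correlation is near zero, they stay essentially as they are.

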5.1. Designing

Phase IV clinical trial, open, non-randomized (or quasi-experimental) prospective trial.

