The shell with low bleed treatment are a contribution to the reduction of the transudation of silicone by osmosis, by the barrier of the elastomer membrane, where part of the thickness of the membrane is formed by an inner layer of elastomer especially impermeable to the silicone oils. The textured surface is effective in reducing the occurrence of capsular contracture when compared to the smooth surface, [11-13] by allying with the low bleed shell in the greatest capacity to prevent this clinical condition.

It is up to the physician to select the appropriate size and type of fixation to meet the clinical

Silimed Indústria de Implantes Ltda

[name]

[contact] [contact]

www.silimed.com.br • [contact] • facebook: silimed international/brasil

and aesthetic requirements of each case. They are all supplied sterile and intended for single use. The package should only be opened inside the surgical center, also containing auxiliary glove for implantation.

5.4.2. Descriptive characteristics or that could interfere in the prognosis.

The rationale for conducting a randomized clinical trial is to create "comparable" groups (e.g. standard group / comparison vs. new intervention) such that the effects observed at the end of follow-up can be attributed to intervention. For this purpose, it is necessary to verify, at the beginning of the follow-up, the characteristics that can lead to confounding. This procedure is also performed in non-randomized trials, and additionally these same characteristics may serve as elements to be adjusted, for example in group formation, where the estimation of event rates could be biased due to confounding (e.g. at some point the groups could be considered "non-comparable" given differences in initial characteristics requiring adjustments).

These characteristics will be grouped as follows: (a) clinical characteristics, (b) characteristics related to surgical procedures and wound care, and (c) characteristics related to the intervention / implants.

Examples of clinical characteristics (but not restricted to): age, weight, body mass index, marital status, ethnicity (skin color), instruction / education, comorbidities (e.g. Arterial hypertension, Diabetes Mellitus, Allergies, etc), use of medications, etc.

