5.7. Allocation for treatment

As this study is being characterized as phase IV, and participants are being included after implantation, the allocation of the participant to a type of implant will be performed by the participant's attending physician according to his/her technical judgment considering the reasons for the implantation and clinical characteristics involved in each case, without sponsor interference. There will be no restriction on the shape or size of the implant.

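### For continuous secondary scores, Section 5.9 names no covariate besides follow-up time, so a gap between the two implant curves may reflect patient differences rather than the implant

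*Combined protocol and SAP*

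**What the plan says.** Section 5.1 describes the design as "Phase IV clinical trial, open, non-randomized (or quasi-experimental) prospective trial". Under Section 5.7, "the allocation of the participant to a type of implant will be performed by the participant's attending physician according to his/her technical judgment".

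Section 5.4.2 accepts that the implant groups may turn out not to be comparable at the start. It lists clinical, surgical and implant characteristics and says that "additionally these same characteristics may serve as elements to be adjusted, for example in group formation". The example it gives concerns event rates.

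Section 5.9 carries this into the safety analysis: a multiple model adjusts each group's hazard, for each event of major interest, for the 5.4.2 characteristics.

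The next paragraph of 5.9 deals with the secondary outcomes "that will be measured as continuous scales will be analyzed as trajectories over time". It sets out three steps: individual crude trajectories; means or medians with confidence intervals at each time; and "finally the marginal trajectories adjusted for correlation of each group (formed by each type of implant - textured and polyurethane"), "always having the follow - up time as a predictor". The Executive Summary describes the same analysis: "changes in scores over time will be used to construct gross and adjusted correlation trajectories". In both places the adjustment is for correlation between repeated measurements, not for differences between patients.

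**The concern.** Two adjacent paragraphs of 5.9 treat the same non-randomised groups differently. Event hazards are adjusted for patient and surgical characteristics. Score trajectories by implant type are not, and no reason is given. Characteristics such as age, body mass index and education can plausibly influence both the physician's choice of implant and how a woman rates her breasts or her self-esteem.

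Post-operative enrolment makes this harder to repair. Inclusion criterion 4 in 5.3.1 admits women up to 14 days after implantation, and the first questionnaires are completed at Visit 1. A change from Visit 1 is therefore a change from a score already taken with the implant in place, and it cannot remove differences that existed before surgery. The recorded patient characteristics are the main protection available.

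The secondary objective is implant performance, judged through satisfaction and quality of life. If a reader sets the two curves against each other, a gap could be credited to an implant surface when it belongs to the women who received it.

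**Working it through.** **Comparison of the passages**

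| Item | Event hazards (5.9) | Continuous secondary scores (5.9) |
|---|---|---|
| Groups | Implant type | Implant type |
| How formed | Physician's choice (5.7) | Physician's choice (5.7) |
| Named adjustment | 5.4.2 characteristics | Correlation between repeated measures |
| Named predictor | Group and 5.4.2 characteristics | Follow-up time, within each group |
| Pre-operative value | Not applicable | None (5.3.1) |

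The permission in 5.4.2 is general (the characteristics may be used for adjustment), but 5.9 puts it into effect only for events.

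**Size of the possible bias**

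The plan gives no SD, effect, imbalance or precision target for the secondary scores, so there is no figure of its own to reproduce. What follows is an illustration.

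Inputs:
- Group size at entry: 350 per implant type (5.10).
- Group size at 10 years: with the 40% loss assumed in 5.10, 350 × 0.60 = 210.
- Imbalance of one covariate between groups, d: 0.25 to 0.5 SD (assumed).
- Correlation of that covariate with the score, r: 0.2 to 0.4 (assumed).

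If a one-SD difference in the covariate moves the score by r SD, the unadjusted gap shifts by d × r:
- 0.25 × 0.2 = 0.05 SD
- 0.25 × 0.4 = 0.10 SD
- 0.5 × 0.2 = 0.10 SD
- 0.5 × 0.4 = 0.20 SD

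For a difference in means at one visit, with a common SD and n women per group, the 95% half-width is 1.96 × √(2/n):
- n = 350: 1.96 × √(2/350) = 0.148 SD
- n = 210: 1.96 × √(2/210) = 0.191 SD

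Bias relative to the half-width:
- n = 350: 0.05/0.148 = 0.34, up to 0.20/0.148 = 1.35
- n = 210: 0.05/0.191 = 0.26, up to 0.20/0.191 = 1.05

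So the shift runs from about a quarter of the half-width to somewhat above it. Widening the assumptions to r = 0.1 to 0.5 and d = 0.2 to 0.5 gives shifts of 0.02 to 0.25 SD, which range from negligible to serious. This treats one covariate; several could add up or cancel.

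**The case against.** The strongest reply is that the comparison at risk is not in the plan. Section 4.2 aims to estimate performance. Section 5.9 estimates a trajectory for each group and states no between-implant contrast, test or margin for the scores. Section 5.10 sizes the groups for precision of event risks within each group, and Section 13 sets the expected benefit against a desired measure, not one implant against the other. This stands. Each crude curve is a valid description of the women observed with that implant, and confounding enters only when a gap is attributed to implant type. The concern survives because the curves are formed by implant type, 2.3 cites the lack of direct comparison between surfaces, and nothing in 5.9 tells the reader not to compare them.

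Several stronger readings are tempting but not supported:

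- **Time is the only predictor allowed.** The text makes time a predictor in every model. It does not exclude others, and 5.4.2 permits adjustment in general terms. This is an omission, not a prohibition.
- **The satisfaction ratings are covered too.** Section 5.6.3 uses a five-category item, while 5.9 refers to continuous scales. Whether the trajectory plan applies to satisfaction is unclear.
- **The analysis mishandles dropout.** Section 5.9 names no estimator. Marginal trajectories could come from a likelihood mixed model or from estimating equations, and these differ in their sensitivity to dropout. Section 5.10 does ask whether loss is differential, although its scenarios (outcome present or absent) suit events better than scores.
- **The bias can be as wide as the whole interval.** The figures 0.148 and 0.191 SD are half-widths. The full widths are 0.296 and 0.382 SD, so the largest assumed bias of 0.20 SD is 68% and 52% of them.
- **Everything in 5.4.2 should be adjusted for.** Placement technique, incision and implant size belong to the same surgical decision as the implant. Adjusting for them could remove part of a real difference in performance.

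**Conclusion.** The point holds as a gap in specification. For continuous secondary scores by implant type, no covariate other than follow-up time is named, although the physician chooses the implant, 5.4.2 accepts possible non-comparability, and the same section adjusts event hazards. The crude curves stand as descriptions of each group, but a gap between them cannot be read as an effect of the implant.

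The size cannot be derived from the documents. Under the assumed imbalance and correlation, the gap shifts by 0.05 to 0.20 SD, against a half-width of 0.15 SD (350 per group) to 0.19 SD (210 per group). At the upper end the bias is as large as the sampling uncertainty or larger; at the lower end it matters little. The present plan would not show which applies. The change is worth making because it uses data already collected and gives up nothing now planned.

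**What to change.** Add to Section 5.9, for secondary outcomes measured as continuous scales:

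1. Keep the crude curves and state that they are descriptive and not for comparing implants.
2. Add a longitudinal model with implant type, time, their interaction and the pre-implant patient characteristics of 5.4.2 (age, body mass index, education, marital status, ethnicity, comorbidities). Report each implant's curve standardised to the pooled sample, with confidence intervals.
3. Put placement technique, incision and implant size in a sensitivity analysis only. Texture and implant type define the groups and should not be covariates.
4. Name the estimator: a likelihood mixed model, or weighted estimating equations if a marginal model is preferred, so that dropout related to recorded factors is handled.
5. State that unmeasured pre-operative differences, including pre-operative scores, remain. The Visit 1 score is post-operative and should not be presented as a pre-operative baseline.
6. Say whether the five-category satisfaction item falls under this analysis and, if not, how it is analysed.

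The cost is a few lines of SAP text and some code. The socio-demographic, vital-sign and surgical forms are already part of Visit 1, and the eligibility evaluation in 6.3 records weight, height and disease history. No new data, visits or participants are needed.
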